8. STATISTICAL ANALYSIS METHODS

If not otherwise specified, statistical significance is defined as $p < 0.05$ and is two-tailed. Data will be summarized with respect to demographic and baseline characteristics and safety

NOVUM PHARMACEUTICAL RESEARCH SERVICES
STATISTICAL ANALYSIS PLAN

Ketoconazole Cream 2%

Protocol / Study No. 71875502

variables.

For categorical variables, the number and percent of each category within a parameter will be calculated. For continuous variables, statistics will include n, mean, standard deviation, median and range.

All statistical analyses will be conducted using SAS®, Version 9.4 or higher. Datasets will be prepared using headings from Clinical Data Interchange Consortium (CDISC) Study Data Tabulation Model (SDTM) implementation for human clinical trials and ADaM (Analysis Dataset Model) and FDA Guidance of Technical Specifications - Comparative Clinical Endpoints Bioequivalence Study Analysis Datasets for Abbreviated New Drug Application (September 2018) .

8.1 Baseline Characteristics

8.1.1 Patient Disposition

The patient disposition information will be summarized by treatment group as well as total. The number of patients randomized will be tabulated by treatment group and total. In addition, completion status and primary reason for withdrawal will be summarized by treatment group and total.

8.1.2 Demographic and Other Baseline Characteristics

Baseline comparability of all treatment groups will be evaluated separately in the PP, mITT and Safety populations.

The following baseline demographics (determined from their initial study visit) will be evaluated:

- Age (years)
- Sex (male/female)
- Ethnicity (Hispanic/non-Hispanic)
- Race (White, Black/African American, Native Hawaiian or Other Pacific Islander, Asian, American Indian or Alaska Native, Other)
- Type of infection (interdigital only or interdigital with extension)
- Total baseline signs and symptoms score
- Presence or absence of onychomycosis
- Number of Tinea Pedis infections in the past 12 months

NOVUM PHARMACEUTICAL RESEARCH SERVICES
STATISTICAL ANALYSIS PLAN

Ketoconazole Cream 2%

Protocol / Study No. 71875502

- Primary infective organism

Summary tables by treatment group will be presented. Continuous variables will be summarized using descriptive statistics (n, mean, standard deviation, median and range). Range will have the same decimal places as raw values. Mean, median and standard deviation will have one decimal place more than that of raw values. Categorical variables will be summarized using frequencies and percentage.

Baseline comparability of the treatments will be presented using Cochran-Mantel-Haenszel (CMH) test for the categorical variables, and Analysis of Variance for the continuous variables.

All data will be listed by treatment group and patient.

8.1.3 Medical History

At Visit 1, Patients will also be questioned about personal medical history, including tinea pedis history.

Medical history data will be listed by treatment group and patient.

8.2 Efficacy Analyses

8.2.1 Efficacy Analyses on Primary and Secondary Endpoints

Therapeutic Equivalence

Therapeutic equivalence will be evaluated for the primary endpoint in the per-protocol (PP) population. If the 90% confidence interval (calculated using Yates' continuity correction) on the absolute difference between the proportion of patients with a Therapeutic Cure in the Test and Reference groups ($p_T - p_R$) is contained within the range [-20%, +20%] then therapeutic equivalence of the Test product to the Reference product will be considered to have been demonstrated.

The same statistical approach will be conducted for analyses of the secondary endpoints in the PP population.

To declare therapeutic equivalence of the Test product to the Reference product, equivalence must be demonstrated for only the primary endpoint in the PP population.

Patients who are missing mycological culture data at the test-of-cure visit will not be included in the analysis for the secondary endpoint of Mycological Cure.

Superiority to Placebo

NOVUM PHARMACEUTICAL RESEARCH SERVICES
STATISTICAL ANALYSIS PLAN

Ketoconazole Cream 2%

Protocol / Study No. 71875502

Superiority of the Test and Reference products against the Placebo product for the primary endpoint will be evaluated in the mITT population using, if necessary, LOCF as described in section 11.3.2 of the protocol.

Patients discontinued early for reasons other than lack of treatment effect will be excluded from the PP population and included in the mITT population using LOCF. Patients who qualify for inclusion in the mITT population with missing endpoint data who were not discontinued for lack of treatment effect will also be evaluated using LOCF; that is, if a patient who was not discontinued for lack of treatment effect does not have KOH or mycological culture results at Visit 3, this patient will be evaluated for the primary and secondary endpoints using LOCF from Visit 1. Patients who discontinued because of lack of treatment will not have LOCF performed.

Patients who meet the criteria above, but who also used topical drug therapy on the feet for the treatment of irritation or pruritus after the treatment phase of the study will be included in the mITT as Therapeutic Failures. If no mycological testing is performed, these patients will be considered Therapeutic Failures in the primary analysis but the Mycological Cure data will be set to missing for the secondary endpoint. No LOCF will be performed.

If the proportions of patients with a Therapeutic Cure in the Test and the Reference product groups are numerically and statistically superior to that of the Placebo ($p < 0.05$; using a two-sided Cochran-Mantel-Haenszel [CMH] test, stratified by clinical site) then superiority of the Test and Reference products over Placebo will be concluded.

The same statistical approach will be conducted for analyses of the secondary endpoints in the mITT population.

To declare superiority of the Test and Reference products over Placebo, their superiority must be demonstrated for only the primary endpoint in the mITT population.

Treatment-by-Site Interaction and Pooling of Clinical Sites

As this is a multiple-site study, the interaction of treatment-by-site may be evaluated for the primary efficacy endpoint in the PP population for equivalence testing. The treatment-by-site interaction will be evaluated by the Breslow-Day test for homogeneity of the odds ratio at the 5% significance level ($p < 0.05$, 2-sided). A site(s) with a low enrollment rate(s) may be pooled with its geographically closest site, so as to avoid bias in the stratification of the sites in the CMH test and in the estimation of a treatment-by-site interaction effect. The pooling will be done for low enrolling sites that account for less than 4-7% of the total number of patients in the PP population at the site with the highest enrolling rate in the PP population. If the treatment-by-site interaction term is found to be statistically significant ($p < 0.05$) for the primary endpoint, then the interaction term will also be assessed for clinical relevance before pooling the data across sites. This will include examination of Therapeutic Cure rates at each site where sample sizes per treatment may be influential in the assessment of the interaction. The treatment-by-site

NOVUM PHARMACEUTICAL RESEARCH SERVICES
STATISTICAL ANALYSIS PLAN

Ketoconazole Cream 2%

Protocol / Study No. 71875502

interaction may also be evaluated for the analyses of the secondary endpoints in the PP population for equivalence testing if the treatment-by-site interaction is found to be significant in the primary analysis.

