10.5.3 Visit 3 (Day 56 ± 4 Days): Test-of-Cure/End of Study

1. **Perform Pregnancy Test:** A urine pregnancy test will be required of all female patients of childbearing potential.
2. **Record Vital Signs:** The patient's vital signs will be recorded (blood pressure, pulse, temperature and respiration rate).
3. **Review and Assessment of Concomitant Medications:** Review the patient's use of any new or ongoing concomitant medications since last visit.
4. **Review and Assessment of Adverse Events:** Patients will be questioned about any health status changes/AEs since last visit. All AEs will be recorded.
5. **Assess Local Signs and Symptoms:** Clinical signs and symptoms of tinea pedis at the target lesion site identified at Visit 1 will be evaluated using the static scale in Appendix A. Wherever possible, the same Investigator should attempt to perform all clinical exams at all visits for an individual patient.
6. **Collect Sample for KOH Wet Mount:** Patients with positive baseline culture results will have a sample for the KOH wet mount obtained from the designated target lesion site as per

CONFIDENTIAL PROTOCOL

A Randomized, Double-Blind, Vehicle-Controlled, Parallel-Design, Multiple-Site Clinical Study to Evaluate the Therapeutic Equivalence of Ketoconazole Cream 2% (Encube Ethicals Pvt Ltd) to Ketoconazole Cream 2% (G&W Laboratories Inc.) in the Treatment of Tinea Pedis

instructions in section 10.6.9. The KOH wet mount review should be performed by the Investigator or appropriately trained and qualified delegated staff.

7. **Collect Sample for Mycological Culture:** Patients with positive baseline culture results will have a sample sent to the centralized laboratory for fungal culture. Patients with a positive KOH wet mount at this visit will not have a mycological culture sample collected.
8. **Collect and Review Patient Diary:** Collect previously dispensed diary and review for compliance with the protocol.
9. **Collect Study Product:** Study product tubes that were not returned at Visit 2 will be collected.
10. Discharge from study.

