10.6.11 Collect Sample for Mycological Culture

If, at Visit 1, the patient meets all of the other inclusion/exclusion criteria, including a positive KOH wet mount test, then a sample will be sent to the centralized laboratory for fungal culture. As it could take up to 28 days or more for the results of the fungal cultures to be known, the Investigator can enroll patients into the study if they meet all of the other inclusion/exclusion criteria pending the results of the fungal culture. Culture must be positive for *T. rubrum*, *T. mentagrophytes* or *E. floccosum* for the patient to be included in the modified intent-to-treat (mITT) and per-protocol (PP) populations.

The sample for the culture should be placed into the transport kit provided by the central laboratory. The kit should be sealed according to the directions on the back of the kit itself. The sample kit should be sent to the central laboratory as instructed in the laboratory manual provided by ACM-Pivotal Global Central Laboratory.

ACM Pivotal Laboratory
[name]
[name]
[contact]

If the results of the baseline culture are positive, patients may continue in the study and samples for mycological culture will be obtained from the target lesion site at Visit 3. If the results of the baseline culture are negative, the patient should be discontinued and early termination procedures should be performed. No mycological culture sample should be collected as part of the early termination procedures.

Mycological culture samples will not be collected for patients with a positive KOH wet mount at Visit 3.

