Medical History and Demographics	X		
Perform Pregnancy Test **	X	X	X
Record Vital Signs	X	X	X
Review and Assessment of Concomitant Medications	X	X	X
Review and Assessment of Adverse Events		X	X
Designate Target Lesion	X		
Assess Local Signs and Symptoms	X	X	X
Collect Sample for KOH Wet Mount	X		X [†]
Inclusion/Exclusion Criteria Review	X		
Collect Sample for Mycological Culture [‡]	X		X
Dispense Study Product	X		
Provide Patient Diary	X	X	
Collect/Review Patient Diary		X	X
Collect Study Product		X	X [§]
Discharge from Study			X

*Dosing regimen is once daily for 42 ± 4 days starting on the day of enrollment (Day 1) through the day of Visit 2 (Day 42 ± 4).

** For females of childbearing potential

[†]KOH sample will not be collected if baseline culture is negative.

[‡]Mycological culture sample will not be sent if KOH is negative at baseline or positive at Visit 3. See Appendix B.

[§]Study product will be collected at Visit 3 if it is not returned at Visit 2.

NOVUM PHARMACEUTICAL RESEARCH SERVICES
STATISTICAL ANALYSIS PLAN

Ketoconazole Cream 2%

Protocol / Study No. 71875502

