6. EFFICACY VARIABLES AND EFFICACY ENDPOINTS

Efficacy Variables

The primary and secondary efficacy variables are the outcome of the KOH test (negative or positive), outcome of the mycological culture (negative or positive), and signs and symptoms scores.

Primary Efficacy Endpoint:

The primary efficacy endpoint is the proportion of patients in each treatment group with a Therapeutic Cure of tinea pedis at the test-of-cure visit two weeks after the end of treatment (Day 56 ± 4).

Secondary Efficacy Endpoints:

The secondary efficacy endpoints are:

- The proportion of patients in each treatment group with a Clinical Cure at Day 56 ± 4 .
- The proportion of patients in each treatment group with a Mycological Cure at Day 56 ± 4 .

Definitions

1. **Therapeutic Cure:** To be considered a Therapeutic Cure, the patient must have both Clinical and Mycological Cure of tinea pedis.
2. **Therapeutic Failure:** A patient will be considered a Therapeutic Failure if:

NOVUM PHARMACEUTICAL RESEARCH SERVICES
STATISTICAL ANALYSIS PLAN

Ketoconazole Cream 2%

Protocol / Study No. 71875502

- a. the patient is a Clinical or Mycological Failure
- b. the patient was considered to have an insufficient therapeutic response
- c. the patient used topical drug therapy for irritation or pruritus on the feet between Visit 2 (Day 42 ± 4 days) and Visit 3 (Day 56 ± 4 days)
3. **Clinical Cure:** To be considered a clinical cure the patient's total severity score must be ≤ 2 with no individual severity score > 1 .
4. **Clinical Failure:** A patient will be considered a Clinical Failure if the patient's total severity score is > 2 or any individual score is > 1 .
5. **Mycological Cure:** To be considered a mycological cure the patient must have a negative KOH test and a negative fungal culture.
6. **Mycological Failure:** A patient will be considered a Mycological Failure if the patient's KOH test is positive or the patient's fungal culture is positive.

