7. STUDY POPULATIONS

Per-Protocol Population

The PP population will include all randomized patients who:

- Met all inclusion and exclusion criteria.
- Made the final study visit within the protocol window of Day 56 ± 4 days (Day 52 to Day 60 inclusive) with no protocol violations that would affect the treatment evaluation.
- Did not have any significant protocol deviations.
- Were compliant with dosing between 75%-125% of the required doses.
- Had a positive baseline KOH and fungal culture for *Trichophyton rubrum*, *Trichophyton mentagrophyties* or *Epidermophyton floccosum*.

Patients discontinued from the study because of lack of treatment effect after completing at least 14 days of treatment will be included in the PP population as Therapeutic Failures provided they had a positive baseline KOH, positive baseline fungal culture, and did not have any significant protocol deviations. For these patients, there will be no mycological testing at time of discontinuation; therefore, they will be considered Therapeutic Failures in the primary analysis but the Mycological Cure data will be set to missing for the secondary endpoint.

NOVUM PHARMACEUTICAL RESEARCH SERVICES
STATISTICAL ANALYSIS PLAN

Ketoconazole Cream 2%

Protocol / Study No. 71875502

Patients who meet the criteria above, but who also used topical drug therapy for irritation or pruritus on the feet after the treatment phase of the study will be included in the PP population as Therapeutic Failures. If no mycological testing is performed, the patients will be considered Therapeutic Failures in the primary analysis but the Mycological Cure data will be set to missing for the secondary endpoint.

All analyses performed using the PP population will be done on an observed case basis (i.e., no last observation carried forward [LOCF] will be performed).

Modified Intent-to-Treat Population

The mITT population will include randomized patients who:

- Met all inclusion/exclusion criteria.
- Applied at least one dose of assigned product.
- Had a positive baseline KOH and fungal culture for *Trichophyton rubrum*, *Trichophyton mentagrophyties* or *Epidermophyton floccosum*.

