Patients discontinued early for reasons other than lack of treatment effect will be excluded from the PP population and included in the mITT population using LOCF. Patients who qualify for inclusion in the mITT population with missing endpoint data who were not discontinued for lack of treatment effect will also be evaluated using LOCF; that is, if a patient who was not discontinued for lack of treatment effect does not have KOH or mycological culture results at Visit 3, this patient will be evaluated for the primary and secondary endpoints using LOCF from Visit 1. Patients who discontinued because of lack of treatment effect will not have LOCF performed.

Patients who meet the criteria above, but who also used topical drug therapy on the feet for the treatment of irritation or pruritus after the treatment phase of the study will be included in the mITT as Therapeutic Failures. If no mycological testing is performed, these patients will be considered Therapeutic Failures in the primary analysis but the Mycological Cure data will be set to missing for the secondary endpoint. No LOCF will be performed.

Safety Population

The Safety population will include all randomized patients who use at least one dose of product.

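### The per-protocol Mycological Cure analysis drops patients without a Visit 3 culture, yet culture is withheld by design when KOH is positive, so known failures leave the denominator

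*SAP*

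**What the plan says.** Three provisions bear on the same patient, one who attends Visit 3 and has a positive KOH.

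- **Collection.** Protocol 10.5.3, item 7: "Patients with a positive KOH wet mount at this visit will not have a mycological culture sample collected". Protocol 10.6.11 repeats this: "Mycological culture samples will not be collected for patients with a positive KOH wet mount at Visit 3". The schematic footnote in SAP section 3 agrees: "Mycological culture sample will not be sent if KOH is negative at baseline or positive at Visit 3".
- **Definition.** SAP section 6, definition 6 (also Protocol 11.6): "A patient will be considered a Mycological Failure if" either the KOH or the fungal culture is positive. One positive test is enough.
- **Exclusion.** SAP 8.2.1, under Therapeutic Equivalence, with the same sentence in the Protocol synopsis and Protocol 11.7: "Patients who are missing mycological culture data at the test-of-cure visit will not be included in the analysis for the secondary endpoint" of Mycological Cure.

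SAP section 7 makes all PP analyses observed-case, without LOCF. Elsewhere in that section "the Mycological Cure data will be set to missing for the secondary endpoint" applies to two groups: patients discontinued for lack of effect, and users of topical therapy who had no mycological testing. Neither group covers a KOH-positive completer.

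In the mITT population, a patient without Visit 3 KOH or culture results is handled differently: "this patient will be evaluated for the primary and secondary endpoints using LOCF from Visit 1".

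**The concern.** The exclusion rule depends on whether a culture result exists. By design, a culture result exists only for KOH-negative patients. The rule therefore selects on one component of the outcome: every failure established by a positive Visit 3 KOH leaves, and no cure can leave, because a cure requires a negative culture. The only failures left are KOH-negative patients with a positive culture.

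The plan would also treat one patient in three ways. A KOH-positive completer is a Therapeutic Failure in the PP primary analysis (definition 2a), a Mycological Failure in mITT (Visit 1 KOH and culture are positive by definition of that population), and absent from PP Mycological Cure.

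At stake are the PP rates in table T14.2.11 and their 90% confidence interval, which is judged against the same ±20% range. The rates would be too high in both arms. The difference between arms could shrink, widen or change sign, depending on how KOH-positive failures are distributed.

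**Working it through.** **Inputs from the documents.** 172 PP patients per active arm; planning Therapeutic Cure rates of 45% Test and 50% Reference; power of approximately 85% (SAP section 5). Equivalence requires the Yates-corrected 90% interval to lie within ±20% (SAP 8.2.1).

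**Assumptions.** The documents give no Mycological Cure rate and no Visit 3 KOH-positive share. Therapeutic Cure requires Mycological Cure, so 45% and 50% are a floor for Mycological Cure. Let *m* be the true Mycological Cure rate and *k* the share of mycological failures that are KOH-positive. I take *k* = 0.5, 0.7 and 0.9, keep the documents' 5-point deficit for Test, and assume no other missing data.

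**Step 1: reproduce the plan's power.** With p_T = 0.45, p_R = 0.50 and n = 172:

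- SE = √(0.45×0.55/172 + 0.50×0.50/172) = 0.0538
- Yates term = (1/172 + 1/172)/2 = 0.0058

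Two one-sided tests at 5% give 84.8% by normal approximation and 85.6% by exact enumeration. This agrees with the stated figure.

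**Step 2: rate under the literal rule.** Cures stay and a fraction *k* of failures leaves:

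reported rate = m / [m + (1 − m)(1 − k)]

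For Test with m = 0.65 and k = 0.7: 0.65/(0.65 + 0.35×0.30) = 0.65/0.755 = 86.1%. For Reference with m = 0.70: 0.70/(0.70 + 0.30×0.30) = 0.70/0.79 = 88.6%. Patients removed: 172×0.35×0.7 = 42 and 172×0.30×0.7 = 36.

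**Step 3: range with equal *k* in both arms.** The pass probability is the chance that the interval lies within ±20% (200,000 simulated trials per case).

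| True rates, Test/Reference | k | Reported rates | Pass, full denominator | Pass, as written |
|---|---|---|---|---|
| 65/70% | 0.5 | 79/82% | 89% | 96% |
| 65/70% | 0.7 | 86/89% | 89% | 99% |
| 65/70% | 0.9 | 95/96% | 89% | >99% |
| 45/50% (floor) | 0.5 | 62/67% | 86% | 77% |
| 45/50% (floor) | 0.7 | 73/77% | 86% | 82% |
| 45/50% (floor) | 0.9 | 89/91% | 86% | 98% |

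At 65/70%, the failures removed (Test/Reference) are 30/26, 42/36 and 54/46. At the floor the pass probability can fall, because patients are lost.

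**Step 4: unequal *k* at 65/70% (true difference −5.0 points).**

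- k = 0.7 Test, 0.5 Reference: 86.1 − 82.4 = +3.7 points.
- k = 0.5 Test, 0.7 Reference: 78.8 − 88.6 = −9.8 points.

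**Step 5: one worked table.** Suppose 40% of Test and 20% of Reference patients are KOH-positive, and 10% of the KOH-negative patients have a positive culture.

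- Failures kept: 93/172 (54.1%) v 124/172 (72.1%), difference −18.0, interval −27.0 to −9.0, outside the range.
- As written: 93/103 (90.3%) v 124/138 (89.9%), difference +0.4, interval −6.8 to 7.7, inside the range.

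This is a deliberately large imbalance. It shows that the rule can reverse the finding, not that it is likely to.

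**The case against.** The strongest reply is that missing should be read as due but not obtained. Definition 6 already settles the KOH-positive patient, and for topical-therapy users SAP section 7 sets the endpoint to missing only when no mycological testing was done; a KOH is mycological testing. That may well be what the authors meant. But the sentence refers to culture data rather than mycological status, neither document defines missing here, and the shell for T14.2.11 has no note on N. A programmer filtering on an absent Visit 3 culture would be following the SAP. If the softer reading is intended, the fix only writes it down.

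Second, the direction of the effect on equivalence rests on assumed shares. This stands. If the KOH-positive share of patients (*q*), rather than of failures, is equal in both arms, the difference becomes d/(1 − q) and widens. At 45/50% with q = 0.2 it goes from −5.0 to −6.25 points, and the pass probability falls from 86% to 71%. Only the inflation of the rates is certain.

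Third, the consequence is limited: "equivalence must be demonstrated for only the primary endpoint in the PP population", and the reduced N would be visible in T14.2.11. This also stands.

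Fourth, the mITT LOCF sentence, read equally literally, could carry Clinical Cure forward from Visit 1 for a KOH-positive completer. That arises from a different rule, which this sentence does not create and the fix does not worsen.

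**Conclusion.** The concern holds. Taken together, the collection rule, the failure definition and the exclusion rule remove known failures from PP Mycological Cure, and nothing in either document exempts them. The rates are inflated in both arms whenever any completer is KOH-positive at Visit 3. In the 65/70% example the inflation is about 12 to 30 points (79 − 65 = 14 to 95 − 65 = 30 for Test; 82 − 70 = 12 to 96 − 70 = 26 for Reference).

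The main harm is wrong reported rates. Near the planning difference the equivalence reading for this endpoint would usually be the same, though it can move either way. These sizes depend on assumed mycological rates and KOH shares.

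The primary endpoint, its power, the formal equivalence decision and the mITT superiority analysis are unaffected: KOH-positive patients remain Therapeutic Failures, and in mITT they remain Mycological Failures. This should be fixed, but it does not threaten the trial's main conclusion.

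**What to change.** In SAP 8.2.1, and in the matching text of the Protocol synopsis and Protocol 11.7, replace the exclusion sentence with:

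> A patient with a positive KOH or a positive culture at Visit 3 is a Mycological Failure and is included in the Mycological Cure analysis, whether or not the other test was done. In the PP analysis, patients are excluded only if mycological status cannot be determined (negative KOH with no culture result, negative culture with no KOH result, or neither result). The mITT LOCF rules are unchanged.

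Add a note to T14.2.11 that defines N in the same way. Make the change before database lock, so that the denominator is not chosen with results in view.

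The cost is a short text change. No new data are needed, and the primary and mITT analyses do not change. Reported PP mycological cure rates will be lower than under the literal rule. Protocol 12.2.3 requires IRB review of a protocol revision; if that is not wanted for this point alone, SAP 8.7 already exists to record departures from the protocol's analysis text.
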